6. TRIAL POPULATION AND DESCRIPTIVE ANALYSES

6.1 Representativeness of Study Sample and Patient Throughput

The flow of participants through each stage of the trial, including numbers of participants assigned to a schedule, receiving intended treatment, completing the study protocol, and analysed for the primary outcome is provided following CONSORT. Protocol violations/deviations and information relating to the screening data including the number of ineligible patients entering the study, together with reasons will be reported. Information on number of participants screened, found to be ineligible (with reasons where available), refused to participate (with reasons where available) will also be included.

A CONSORT diagram will be prepared for each stage. Figure 3 represents an example CONSORT diagram.

Figure 3: Example CONSORT Diagram

A phase I dose escalation safety study combining the ATR inhibitor VX-970 with chemoradiotherapy in oesophageal cancer using time to event continual reassessment method (funded by CRUK and Merck)
EudraCT Number: 2015-003965-27

6.2 Withdrawal from treatment and/or follow-up

The Trial Office should be informed of any early patient withdrawal within 24 hours of the site becoming aware as described in the Protocol, Section 6. Withdrawals will be summarised, at each stage, but no formal assessments will be performed.

6.2.1 Treatment Withdrawal

During the course of the trial, a patient may withdraw early from treatment. This may happen for a number of reasons, including:

- Unacceptable toxicity
- AE/SAEs requiring discontinuation
- Loss to follow-up
- Significant protocol deviation or inability to comply with trial procedures
- Clinical decision
- Patient decision

The end of treatment means the patient will then enter the routine follow up stage of the trial. If M6620 treatment is stopped, the patient will continue with standard treatment and will be followed up as part of the trial.

6.2.2 Consent Withdrawal

Consent withdrawal means that a patient has expressed a wish to withdraw from the study altogether. Under these circumstances, the site needs to document all relevant discussions in the patient notes and notify the Trial Office, which will allow the office to mark all future CRFs as not applicable. The site should inform the Trial Office whether any samples already collected for the study should be destroyed.

Under these conditions, investigators are still responsible to follow up any SAEs until resolution.

6.3 Baseline Comparability of Randomised Groups

Baseline characteristics will be reported for each stage, including important prognostic, demographic and clinical variables.

Numbers (with percentages) for binary and categorical variables and means (and standard deviations), or medians (with lower and upper quartiles) for continuous variables will be presented.

6.4 Unblinding

The trial is not blinded.

6.5 Description of Compliance with Intervention

Patients will be instructed to keep a record of compliance in terms of their capecitabine treatment, by means of using a study patient diary card provided to the patient by the site. Patients should be asked to bring completed diary cards or other records and all their unused / remaining capecitabine tablets (empty, open or unopened) with them to each clinic visit. The patient diary cards should not be sent to the Trial Office but kept by the centre to monitor patient drug compliance. Compliance of M6620 and Cisplatin will be monitored by the patient record.

Accountability logs are required for capecitabine to determine that patients have received at least 80% of the prescribed treatment dose. Returns should be reconciled against the patient diary and the reason for any

A phase I dose escalation safety study combining the ATR inhibitor VX-970 with chemoradiotherapy in oesophageal cancer using time to event continual reassessment method (funded by CRUK and Merck)
EudraCT Number: 2015-003965-27

discrepancy documented. Site staff will collect and count patient returns, which must be recorded on the drug accountability log.

Compliance with all study treatments will be summarised for each stage using proportions calculated with respect to the total dose prescribed.

6.6 Reliability

Data derivation/manipulation will be checked to ensure validity of the derived data, where appropriate. Calculations performed using the computer can be checked by hand for the smallest of 5% or 20 observations within the dataset, where appropriate.

7. ANALYSIS

7.1 Outcome Definitions

A table presenting the objectives, outcome measures and evaluation time points for each stage can be found in Section 2.2 of this document.

7.2 Analysis Methods

7.2.1 Primary Outcome (All Stages)

The primary outcome at each stage is to determine the best tolerated treatment schedule of M6620 administered concomitantly with radiotherapy and/or chemotherapy (depending on the stage). The TiTE-CRM model will be used to achieve this as described in Section 1.13. Results will be presented as posterior probabilities and 95% credible intervals of the schedule-toxicity curve, both in tabular form and graphically.

7.2.2 Secondary Outcomes

Safety and Toxicity Profile of the M6620 (All Stages)

The number (proportion) of patients who have had an AE recorded should be reported by schedule group. The number (proportion) of patients who have experienced one, two, three or more AEs will also be provided by schedule group. It is intended that the number of AEs recorded, the number of AEs per grade and the outcome will be reported.

This analysis will be repeated twice: once using serious adverse events (SAEs) and once using serious adverse reactions (SARs). Note: SARs are SAEs that are recorded as being possibly, probably or definitely related to a component of treatment. For SARs, the treatment component the event was related to may also be described.

Details of any SUSARs will be reported in the statistical report; the schedule group for the affected patient will be indicated.

Dose limiting toxicities are classed as SAEs in CHARIOT and will be analysed as described above. Length of time for toxicities to resolve will also be summarised and presented as mean (SD) or median (IQR).

Proportion of patients completing planned dose (All Stages)

To determine the ability to deliver the M6620 with palliative radiotherapy (Stage A1) and palliative chemotherapy (Stage A2), the proportion of patients completing at least 75%, 90% and 100% of the planned dose will be tabulated by schedule group.

A phase I dose escalation safety study combining the ATR inhibitor VX-970 with chemoradiotherapy in oesophageal cancer using time to event continual reassessment method (funded by CRUK and Merck)
EudraCT Number: 2015-003965-27

To determine tolerance and ability to deliver M6620 in combination with standard definitive chemoradiotherapy in Stage B, the proportion of patients completing at least 80% of the planned chemotherapy dose and at least 20 fractions of radiotherapy will be tabulated by schedule group.

Efficacy of the combination (All Stages)

Objective tumour response will be classified according to the RECIST v1.1 criteria. The number and proportion of patients who achieve Complete Response (CR), Partial Response (PR), (Stable Disease) SD and Progressive Disease (PD) will be reported overall and by treatment schedule.

Overall survival (OS) will be presented by stage using Kaplan Meier graphs along with two-sided 95% confidence intervals. Median and quartile OS will also be presented together with their 2-sided 95% confidence intervals if applicable.

Progression free survival (PFS) will be presented overall by stage using Kaplan Meier graphs along with two-sided 95% confidence intervals. Median and quartile PFS will also be presented together with their 2-sided 95% confidence intervals if applicable.

In field radiotherapy control (Stage A1)

This will be assessed and measured via CT scan response and/or clinical assessment.

Note: *The final statistical report should also include information on the number of participants used in each analysis model, and for the analysis of longitudinal follow-up data, the number of observations used.*

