Physical Exam ⁶	X		X	X	X	X	X	X	X	X	X	X	X	X	X	X
Weight ⁶	X		X	X	X	X	X	X	X	X	X	X	X	X	X	X
Vital signs	X								X ⁸							
ECG ⁷	X		X			X			X			X				
Audiogram monitoring ¹³		X				X										
Concurrent medications ⁶	X		X	X	X	X	X	X	X	X	X	X	X	X	X	X
DLT Assessment ⁶			X	X	X	X										
AE Assessment ⁶			X	X	X	X	X	X	X	X	X	X	X	X	X	X
CT chest abdomen pelvis ⁹	X							X						X		X

¹ Screening assessments including: pregnancy test (to be repeated for WOCBP 4 weekly during treatment), height and medical history, see section 5.3

² Capecitabine taken bd weeks 1 to 18

³ Cisplatin given on day 1 (Mon)

⁴ M6620 (Berzosertib) given on day 2 only (Tues) dose schedules 1 & 3; M6620 (Berzosertib) given on day 2 & day 5 (Tues/Fri) dose schedules 2 & 4

⁵ Check Haem/Biochem within 72 hours prior to cisplatin and 24 hours preceding M6620 (Berzosertib) (only one sample needs to be taken if it satisfies both Cisplatin and M6620 (Berzosertib) requirements): Hb, ANC, lymphocytes, WBC, Platelets, Bilirubin, ALP, AST or ALT, Serum creatinine, Urea, K⁺, Na⁺, eGFR, Ca, Mg, Phosphate

M6620 (Berzosertib) M6620 (Berzosertib)⁶ Assessment done within 24 hours prior to M6620 (Berzosertib) dosing (weight once weekly)

⁷ ECG to be carried out at screening, pre-treatment and once per cycle

⁸ Per clinical requirement

⁹ CT chest abdomen pelvis in weeks 6, 12, 18 and at 8 weeks post EOT. Screening CT only needs to be done if staging CT was carried out > 35 days prior to start of treatment.

¹⁰ Patients can continue with treatment after 4 cycles if CT shows no progression and at the discretion of the PI.

¹¹ Two week follow-up should be 2 weeks after last dose (+/- 7 days); 8 week follow-up should be 8 weeks after last dose (+/- 2 weeks)

¹² If required.

*Each cycle lasts 3 weeks

Repeat assessments
done for cycles 3-4 in
cycles 5-6 (if
applicable)

SUMMARY SCHEDULE OF EVENTS STAGE B

¹Screening assessments including: pregnancy test (to be repeated for WOCBP 4 weekly during treatment), height, medical history, Echo/MUGA and Lung function test, see section 5.3

² Capecitabine taken bd weeks 1 to 6; capecitabine taken bd Mon to Fri weeks 7 to 11

³ Check Haem/Biochem within 72 hours prior to cisplatin and 24 hours preceding M6620 (Berzosertib) (only one sample needs to be taken if it satisfies both Cisplatin and M6620 (Berzosertib) requirements): Hb, ANC, lymphocytes, WBC, Platelets, Bilirubin, ALP, AST or ALT, Serum creatinine, Urea, K⁺, Na⁺, eGFR, Ca, Mg, Phosphate

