2.4 Duration of patient participation

Stage A1: Participants will be in the study for 12 weeks from first trial dose or intervention to last protocol visit.

[figure not shown]
Stage A2: Participants will be in the study for maximum of 26 weeks from first trial dose to last protocol visit.

Stage B: Participants will be in the study for 24 weeks from first trial dose or intervention to last protocol visit.

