5.4.5 Stage A2 evaluations on early withdrawal

Where possible, patients will be followed up as per the follow up visits at 2 and 8 weeks post end of treatment, including assessments of AEs and DLTs (see section 6).

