5.4.6 Stage A2 off-Study and Follow-up Evaluations

The final study visit will occur 8 weeks after completion of treatment. Patients should be counselled on the continued use of contraception for 6 months following the end of treatment **if appropriate** and encouraged to report any pregnancies to the study team. The clinician in charge will be asked to provide the following reports at 6 & 12 months.

- date and cause of death, if applicable
- date and site of progression
- details of any clinically significant events
- further chemotherapy or other intervention required

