8.2 Stage A2 Treatment

Two dose levels and 2 dosing frequencies (treatment schedules) are proposed. Both the dose and frequency of M6620 (Berzosertib) will vary but the Cisplatin and Capecitabine dose and schedule will remain unchanged across treatment plans. The treatment schedule will last for 6 cycles (18 weeks).

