14.9 Reporting Adverse Events on the CRF

All AEs, including Serious AEs must be recorded on the case report forms (CRF) for that patient (unless otherwise specified in section 14.10). The information provided will include date of onset, event diagnosis (if known) or sign/symptom, severity, time course, duration and outcome and relationship of the AE to study drug. Any concomitant medications or any other therapy used to treat the event must be listed. The Investigator will provide an “other” cause for serious AEs considered to be unrelated to the study drug. Sites should ensure data entered into the CRF is consistent with the SAE report information where applicable.

Each separate AE episode must be recorded. For example, if an AE resolves completely or resolves to baseline and then recurs or worsens again, this must be recorded as a separate AE. For AEs to be considered intermittent, the events must be of similar nature and severity.

AEs occurring from the first dose of study medication up to the end of study visit must be recorded on the CRF. AEs may be spontaneously reported by the patient and/or in response to an open question from study personnel or revealed by observation, physical examination, or other diagnostic procedures. Any clinically relevant deterioration in laboratory assessments or other clinical finding is considered an AE. AEs which result in early withdrawal must be reported using the Early Withdrawal Form.

Terms and Grading of Events

All adverse events and toxicities must be graded according to the NCI Common Terminology Criteria for adverse events (NCI-CTCAE) Version 4.0 (currently up to Version 4.03).

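### Stage A2 AE tables by schedule mix observation windows of about 14 to 26 weeks, so they can understate the AE burden of a schedule whose patients stop all treatment early

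*SAP*

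**What the plan says.** **Recording window.** Protocol 14.9 sets the AE period: "AEs occurring from the first dose of study medication up to the end of study visit must be recorded on the CRF". For Stage A2, Protocol 5.4.6 fixes that visit relative to the patient's own treatment: "The final study visit will occur 8 weeks after completion of treatment". The anchor stays the same after early withdrawal, where "patients will be followed up as per the follow up visits at 2 and 8 weeks post end of treatment" (Protocol 5.4.5, where possible). The Stage A2 schedule of events allows 2 weeks either side of the 8-week visit.

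**Treatment length.** Protocol 8.2 plans six cycles, 18 weeks. The last two are conditional: "Patients can continue with treatment after 4 cycles if CT shows no progression and at the discretion of the PI" (schedule of events, Stage A2). Protocol 6.1 lists toxicity, clinical decision and patient decision among the reasons for stopping earlier. Protocol 2.4 gives the outer limit: "Participants will be in the study for maximum of 26 weeks from first trial dose to last protocol visit".

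**Analysis.** SAP 7.2.2 states: "The number (proportion) of patients who have had an AE recorded should be reported by schedule group". It adds the proportions with one, two, three or more AEs and the number of AEs, and repeats the layout for SAEs and SARs. It plans no patient-time denominator, common window or time-to-event summary for AEs. Protocol 18.1 promises a description of follow-up time, but not by schedule and not as a denominator. SAP 6.2 summarises withdrawals by stage only.

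**The concern.** How long a Stage A2 patient is observed for AEs depends on how long that patient stays on treatment, which the schedule itself can influence. A crude count or proportion rises with time observed. If patients on one schedule tend to stop all treatment early, their column is built from shorter windows and fewer weekly on-treatment assessments, and nothing in the table shows it.

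The safety profile is a stated secondary objective of Stage A2, evaluated during weeks 1-18 and at weeks 20 and 26. Those later time points fit only a patient who received all 18 weeks. Readers will compare the schedule columns, and a difference in observation time could be read as a difference in toxicity, or could hide one.

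The SAP handles unequal observation elsewhere: the TiTE-CRM weights DLT-free patients by time observed and dose received, and OS and PFS use Kaplan-Meier.

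**Working it through.** **1. The plan's own figure.** Treatment weeks + 8 = 18 + 8 = 26 weeks, which matches the maximum in Protocol 2.4.

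**2. Windows from the documents.** Window = week in which all treatment stops + 8.

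| Last treatment week | AE window (weeks) | Share of full window |
|---|---|---|
| 4 | 12 | 46% |
| 6 | 14 | 54% |
| 12 (four cycles) | 20 | 77% |
| 18 (six cycles) | 26 | 100% |

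**3. Upper-end illustration: stopping unrelated to the counted event.** The documents give no AE rates, so the weekly hazard h of a first grade 3+ event is an assumption, held constant on and off treatment and equal on both schedules. Crude proportion = 1 − exp(−h × window).

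| h | All complete (26 weeks) | All stop at week 6 (14 weeks) | Difference |
|---|---|---|---|
| 0.02 | 1 − exp(−0.52) = 41% | 1 − exp(−0.28) = 24% | 16 points |
| 0.03 | 1 − exp(−0.78) = 54% | 1 − exp(−0.42) = 34% | 20 points |
| 0.05 | 1 − exp(−1.30) = 73% | 1 − exp(−0.70) = 50% | 22 points |

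Differences are taken before rounding. The early-stopping schedule would need a weekly rate 26/14 = 1.86 times higher before its crude proportion matched the other; for stops at week 12 the factor is 26/20 = 1.30.

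**4. Partial early stopping.** Let the comparison schedule show 50% over 26 weeks (h = ln 2 / 26 = 0.0267), and let half the patients on the more toxic schedule stop at week 6.
- True rate ratio 1.25: average of 58.0% (26 weeks) and 37.3% (14 weeks) = 47.6%. The more toxic schedule looks slightly safer.
- True rate ratio 1.5: average of 64.6% and 42.9% = 53.8%. The excess is attenuated but keeps its direction.

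**5. Stopping caused by the first AE.** Assume AE rates of 0.12 per week (everyone completes) and 0.18 per week (all treatment stops at the first AE).
- *Any AE:* a patient with no AE completes treatment and has the full window, so nothing is lost. 1 − exp(−0.12 × 26) = 95.6%; 1 − exp(−0.18 × 26) = 99.1%. The order is correct and there is no bias.
- *Mean window, higher-rate schedule:* (1 − exp(−0.18 × 18))/0.18 + 8 = 13.3 weeks, against 26.
- *Mean AE count:* 0.12 × 26 = 3.12, against 0.18 × 13.3 = 2.40. The order is reversed.
- *Three or more AEs:* lower rate, 1 − exp(−3.12)(1 + 3.12 + 3.12²/2) = 60%. Higher rate: 96.1% stop and need two more events in 8 weeks (probability 0.422), and 3.9% reach week 18 free of AEs and need three (0.176), giving 0.961 × 0.422 + 0.039 × 0.176 = 41%. The order is reversed.
- *Lower rates:* at 0.03 and 0.045 per week the mean counts are 0.78 and 0.92, so the mean does not always reverse.

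**6. With patient-time.** In step 5, events per patient-week are 3.12/26 = 0.12 and 2.40/13.3 = 0.18, which is the correct order. If AEs are rarer off treatment, on-treatment and post-treatment time must be kept apart for this to hold.

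**7. Is a weeks 1-6 window covered?** A patient who stops in week 1 has a final visit at about 1 + 8 = week 9, or about week 7 at the early limit of the 2-week tolerance. Both lie beyond week 6. Eleven weeks of observation would need one full 3-week cycle (3 + 8), so it cannot be assumed for everyone.

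**The case against.** The case against giving this much weight is substantial.

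- **Stopping for toxicity does not hide the event.** Protocol 14.5 makes an AE that leads to withdrawal reportable, so the patient already counts in the any-AE proportion. This stands: step 5 shows no bias in that measure.
- **Toxicity often does not close the window.** Under Protocol 6.1, a patient who stops M6620 continues standard treatment and follow-up. Protocol 9.3 and 9.3.1 also provide for continued treatment after a DLT and for dose reduction after week 4. This stands, and limits how often windows shorten.
- **Some collection runs longer.** Protocol 14.7 keeps drug-related SAEs reportable at any later time, and Protocol 2.5 and 5.4.6 ask for late toxicity or clinically significant events at 6 and 12 months. This weakens the point for SARs, but it is much less detailed than scheduled AE assessment.
- **Related information is already planned.** DLTs by schedule (Protocol 18.5) rest on a fixed 4-week window in Stage A2, and dose completion is tabulated by schedule (SAP 7.2.2). These help a reader, but neither gives AE observation time.
- **The groups are tiny.** At most 20 patients over four schedules is about five each, so one patient is worth about 20 points. Chance will often exceed this effect. That argues for modest weight, not for leaving windows unreported.

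Two stronger readings are tempting. A reader might infer that the less tolerable schedule will always look safer; steps 4 and 5 show otherwise. A reader might also infer that these tables bias the MTD. The documents do not support that: the MTD comes from the TiTE-CRM on DLTs, SAP 5.1 sets no significance level, and the AE summaries are descriptive.

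**Conclusion.** The point holds in a limited form. Stage A2 AE windows follow each patient's own last treatment, and the by-schedule summaries take no account of this, so they can understate the AE burden of a schedule whose patients stop all treatment early. The multiple-AE categories and AE counts are exposed whatever the reason for stopping. The any-AE proportion is exposed only when the stop is for something other than the counted AE, such as progression or a patient or clinician decision.

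Only the windows come from the documents. The 16 to 22 points rest on assumed constant hazards, on stopping unrelated to the event, and on the extreme contrast of everyone stopping at week 6 against everyone completing; partial early stopping gives less. This is an inexpensive improvement to secondary reporting, not a fault in the dose-finding design.

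**What to change.** In SAP 7.2.2, for Stage A2, add by schedule:

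1. total and median weeks under AE observation;
2. grade 3+ events per patient-week, split into on-treatment and post-treatment time;
3. the proportion with a grade 3+ event in weeks 1-6, stating how many patients were observed through week 6 and censoring deaths and consent withdrawals.

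Keep the crude table, labelled as not adjusted for observation time.

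The additions use treatment, visit and AE dates already collected and change nothing in treatment, follow-up or dose allocation. The cost is a few extra table rows. The rates will be imprecise with about five patients per schedule and should be presented as descriptive. The weeks 1-6 proportion still mixes weekly on-treatment visits with sparser post-treatment ones for very early stoppers, which a footnote should say.

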2.6 Recruitment Schematic

3 OBJECTIVES AND ENDPOINTS

3.1 Stage A

3.1.1 Stage A1

Primary Objective	Endpoints/ Outcome Measures	Time point(s) for evaluation of end point

 To determine the best tolerated M6620 (Berzosertib) treatment schedule (or phase II recommended dose (RPTD)) administered concomitantly with Radiotherapy only in the palliative treatment of oesophageal cancer 	Highest treatment schedule resulting in less than 25% dose limiting toxicity (DLT) rate (see section 9.1.2 for DLT definitions)	
 Week 9
Secondary Objectives	Endpoints/ Outcome Measures	

 To determine the safety and toxicity profile of M6620 (Berzosertib) administered concomitantly with RT only in the palliative treatment of oesophageal cancer 	
 Any toxicity grade ≥ 3 graded according to CTCAE v4.03 and length of time for toxicity to resolve 	
 During radiotherapy Weeks 1-3 Week 4, 9 and week 12

 To determine if M6620 (Berzosertib) can be delivered in combination with palliative RT 	
 Proportion of patients completing at least 75%, 90% and 100% of the planned RT dose 	
 End of radiotherapy End of Week 3

 Efficacy of the combination 	
 Objective tumour response (OR) as evaluated by CT scan and quantified by Response Criteria Evaluation (RECIST 1.1) PFS and OS from D1 In field radiotherapy control 	
 12 weeks 6 and 12 months
Tertiary Objectives	Endpoints/ Outcome Measures	

 Explore tumour characteristics associated with response 	
 Genotyping of tumours 	
 Pre-trial archival biopsy

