14 SAFETY REPORTING

The Investigator will monitor each patient for clinical and laboratory evidence of adverse events on a routine basis throughout the study. Should an Investigator become aware of any study drug related SAEs following this period these must also be reported as stated below. Adverse event monitoring starts from the time the patient consents to the study until they complete the trial. All reportable AEs will be followed to a satisfactory conclusion. Any reportable drug-related AEs that are unresolved at the end of treatment visit are to be followed up by the Investigator until resolution or stabilisation. All AEs reported to the Trial Office will be processed according to internal SOPs. The Trial Office may request additional information for any AE as judged necessary.

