14.8 Follow-up of Serious Adverse Events

A follow-up report must be completed when the SAE resolves, is unlikely to change, or when additional information becomes available. If the SAE is a suspected SUSAR then follow up information must be provided as requested by the Trial Office.

If new or amended information on a reported SAE becomes available, the Investigator should report this on a new SAE form using the completion guidelines. If using the original form to notify further information, you must initial and date all new or amended information so that all changes are clearly identified.

SAEs that are considered to be definitely unrelated to the trial intervention will not be followed up and monitored.

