20.2 Case reports forms (CRFs)

The Investigator and study site staff will ensure that data collected on each subject is recorded in the CRF as accurately and completely as possible. All appropriate laboratory data, summary reports and Investigator observations will be transcribed into the CRFs from the relevant source data held in the site medical record(s). CRFs entries will not contain any source data (unless otherwise specified in the completion instructions provided by the Trial Office). It is important to ensure that:

- the relevant CRFs are completed.
- all CRF data are verifiable in the source documentation or the discrepancies must be explained.
- CRF sections are completed in a timely fashion, as close to the visit or event being recorded as possible. This trial uses a continual reassessment model for dose escalation, where escalation decisions are made based on all critical toxicity summary data entered to date. It is necessary to enter all participant data as soon as possible to allow accurate assessment of the data and appropriate dose escalation decisions to be made.
- Data queries are resolved and documented by authorised study staff in a timely fashion. The reason for the change or correction should be given where appropriate.
- As much data as possible is entered and cleaned in preparation for each study database lock point.

Note: 'in a timely fashion' means within no more than 5 working days of the initial event and within 14 days of receipt of a data query unless otherwise specified.

If a patient withdraws from the study the Trial Office must be informed within 24 hours using the Early Withdrawal Form, the reason must be noted and the patient must be followed-up as per protocol.

20.3 Accounting for missing, unused, or spurious data.

The statistical analysis plan will describe the procedure for accounting for missing, unused or spurious data.

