7.3 Missing Data

Every effort will be made for complete collection and recording of data. Dose allocation and primary outcome evaluation using the TiTE-CRM model requires complete data; for this reason, a dedicated CRF has been designed, which captures only that data required to run the model.

No data imputation is planned.

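### SAP 7.2.2 summarises time to resolution of toxicity by a plain mean or median, with no rule for events that have no resolution date

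*SAP*

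**What the plan says.** Protocol 3.1.1, 3.1.2 and 3.2 each list, as a secondary endpoint, grade 3 or worse toxicity together with "length of time for toxicity to resolve". SAP 7.2.2 states the method for all stages: "Length of time for toxicities to resolve will also be summarised and presented as mean (SD) or median (IQR". It does not define the value for an event that has not resolved.

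The same SAP section also promises that "the number of AEs per grade and the outcome will be reported", but does not link those outcome counts to the duration summary. SAP 7.3 says only that "No data imputation is planned", although Protocol 20.3 hands the question over: "The statistical analysis plan will describe the procedure for accounting for missing, unused or spurious data".

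On collection, Protocol 14 says that reportable drug-related events unresolved at the end of treatment visit "are to be followed up by the Investigator until resolution or stabilisation". Protocol 14.8 adds: "A follow-up report must be completed when the SAE resolves, is unlikely to change, or when additional information becomes available". It also says that serious events judged definitely unrelated are not followed up. Protocol 14.9 records onset date, duration and outcome, with each episode entered separately.

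**The concern.** Time to resolution is a right-censored quantity. An event that is still open when observation stops has a duration known only to exceed some value, and these open events tend to be the long ones. A mean or median computed from completed durations leaves them out. A mean that treats the last visit as the end date cuts them short. Either way toxicity looks briefer than it is, and the gap widens as toxicity becomes more persistent.

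The SAP handles the same problem properly a few lines later, where overall and progression-free survival get Kaplan-Meier estimates. At stake is how far the descriptive safety profile carried into phase II can be trusted on persistence of toxicity.

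**Working it through.** The documents state no figure for this endpoint, so there is nothing to reproduce. The sample sizes of 18 (A1) and 16 (A2) come from TiTE-CRM simulations and do not depend on it.

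**Step 1: which events can lack a resolution date.**
- Events closed as stabilised or unlikely to change (Protocol 14 and 14.8).
- Events ongoing at death. Stage A is palliative, and Protocol 1.1 cites a median survival of 203 days with radiotherapy alone.
- Serious events judged definitely unrelated (Protocol 14.8).
- Late events open at the cut-off. Stage B late DLTs begin 6 weeks after radiotherapy and the last visit is 13 weeks after it, which leaves at most about 13 − 6 = 7 weeks of scheduled observation. SAP 3.8 allows final analysis once patients reach 3 months (A1) or 26 weeks (A2), and at 24 weeks after the last patient starts (B). Protocol 18.6 gives Stage B up to 12 months.

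**Step 2: resolved events only.** From the documents: treatment lasts 3, up to 18 and 11 weeks in A1, A2 and B (Synopsis), and the last visit is at 12, up to 26 and 24 weeks (Protocol 2.4). Assumed, not in the documents: exponential time to resolution with true median M, onset uniform over treatment, observation ending at the last visit, no deaths. Time under observation is then uniform from a (last visit minus treatment length) to b (last visit): 9–12, 8–26 and 13–24 weeks.

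With λ = ln 2 / M:
- unresolved share u = (e^(−λa) − e^(−λb)) / (λ(b − a))
- resolved-only median = −ln(1 − (1 − u)/2) / λ, valid because every result below is less than a.

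Example, A1 with M = 8: λ = 0.0866, u = (0.459 − 0.354)/(3 × 0.0866) = 0.40, and the median is −ln(1 − 0.298)/0.0866 = 4.1 weeks.

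| True median (weeks) | A1 | A2 | B |
|---|---|---|---|
| 2 | 1.9 (3% unresolved) | 2.0 (1%) | 2.0 (under 1%) |
| 4 | 3.1 (16%) | 3.6 (8%) | 3.7 (5%) |
| 8 | 4.1 (40%) | 5.4 (25%) | 5.8 (21%) |

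A simulation of 200,000 events per cell gives the same values. The Kaplan-Meier median on the simulated data recovers 2.0, 4.0 and 8.0 weeks.

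**Step 3: unresolved events kept, cut at the last visit.** The mean becomes (1 − u)/λ. For A1 with M = 8 this is 0.596/0.0866 = 6.9 weeks, against a true mean of 8/ln 2 = 11.5. The median stays at 8.0, because every event is watched for at least 9 weeks. If deaths are added at an exponential rate with median 203/7 = 29 weeks, the cut median falls to 1/(1/8 + 1/29) = 6.3 weeks and the resolved-only median to 3.8.

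**Step 4: the opposite extreme.** Suppose every event is followed indefinitely and only a share p never resolves, with median 4 weeks among those that do. Counting all events, the median is −4 ln(1 − 0.5/(1 − p))/ln 2, which is 4.7, 5.7 and 7.2 weeks for p = 10%, 20% and 30%. The resolved-only figure stays at 4.0.

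**The case against.** The strongest reply is that the protocol does not stop looking at the last visit. Section 14 has all reportable events followed to a satisfactory conclusion, and drug-related ones to resolution or stabilisation. Protocol 6.2 keeps serious events under follow-up even after consent is withdrawn. Protocol 2.5 collects late toxicity at 6 and 12 months in A1 and A2. The recording window in Protocol 14.9 ("AEs occurring from the first dose of study medication up to the end of study visit must be recorded on the CRF") governs when events start, not how long resolution can be observed. All of this stands, and it means the hard stop in Step 2 exaggerates the loss. It does not supply dates for stabilised events, deaths or events open at the data cut.

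Three stronger readings are tempting but unsupported:
- A reader might infer that the SAP discards unresolved events. It does not say so. That is the natural way to compute a plain mean or median, but a median that keeps open events can be right, as Step 3 shows.
- A reader might infer that persistent toxicity disappears from the report. It remains in the adverse event counts and in the outcome listing.
- A reader might assume onset spread evenly over all 12 weeks of A1. Then u = (1 − e^(−12λ))/(12λ), giving 42% unresolved at a true median of 4 weeks and 62% at 8. That places 9/12 = 75% of onsets after the 3-week treatment and still imposes a hard stop, so it is too severe to serve as the estimate.

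It is also fair to say that at most 20 patients over six A1 schedules will often not support a median per schedule.

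**Conclusion.** The gap is real. A named secondary endpoint is given a method for complete data, while the protocol itself produces incomplete durations. The direction of bias is towards short durations if resolved events alone are used, or if a mean is taken with open events cut at the last visit.

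The size cannot be settled from the documents. On the Step 2 assumptions it runs from negligible at a true median of 2 weeks to roughly a quarter to a half of the median lost at 8 weeks (5.8 to 4.1 against 8.0). Those figures ignore follow-up beyond the last visit, which would reduce them, and deaths, which would increase them. The death rate in Step 3 comes from palliative radiotherapy and should not be carried over to Stage B.

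This is a descriptive safety summary. Schedule allocation, the toxicity stopping rule and the TiTE-CRM use the occurrence of DLTs, not their duration, and are unaffected. The SAP should be corrected, but the trial's main conclusion does not depend on it.

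**What to change.** In SAP 7.2.2, replace the mean or median with a Kaplan-Meier estimate of time to resolution, censored at last assessment, or with the cumulative incidence of resolution treating death as a competing event. Present it by stage, and by schedule where numbers allow, giving the median if it can be estimated. Tabulate unresolved events by schedule as ongoing, stabilised or died. State whether the unit is the event or the patient, since one patient can contribute several episodes.

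Events closed as stabilised need particular care. Censoring them at closure assumes they would go on to resolve like the rest, which is unlikely. The table by reason, or a cumulative incidence that keeps them in the denominator, guards against this.

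The cost is a little extra analysis and a last-assessment date for each ongoing event, which Protocol 14.9 does not list among the recorded items. Some medians will not be estimable: on the Step 2 assumptions with a true median of 16 weeks, 64% of A1 events are unresolved and the Kaplan-Meier median is not reached. SAP 1.2 already commits to an update before Stage B opens, and the change could be made then.
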